9.5.4. Contraception and Pregnancy

Male subjects must continue to use appropriate contraception with their partners, or refrain from sexual activity, as described in Section 6.3.1.

If a male subject makes or believes that he has made someone pregnant during the study, then the Study Center staff must be informed immediately. An Initial Pregnancy Form should be submitted to the Sponsor or designee **within 24 hours** of first learning of the occurrence of pregnancy. Follow-up information including delivery or termination is reported by designating as 'Follow-up' on the Pregnancy Forms and reported within 24 hours.

Payment for all aspects of obstetrical care, child or related care will be the subject's responsibility.

Male subjects: The progress of the pregnancy of a male subject's partner should be followed until the outcome of the pregnancy is known (i.e., delivery, elective termination, or spontaneous abortion). If the pregnancy results in the birth of a child, **the Study Center and Sponsor may follow-up with the mother and may request access to the mother and infant's medical records** to obtain additional information relevant to the pregnancy progress and outcome. A longer follow-up may be required if a newborn child experiences a medical condition, follow-up will be performed to the extent permitted by the applicable regulations and privacy considerations; e.g., partner ICF may be required.

10. STATISTICAL CONSIDERATIONS

10.1. Stratification

Subjects will be stratified based on screening plasma AGT concentration (≤ 30 $\mu\text{g/mL}$ vs. > 30 $\mu\text{g/mL}$).

10.3. Populations

Full Analysis Set (FAS): All randomized subjects who have received at least 1 injection of Study Drug (ISIS 757456 or Placebo) and who have at least 1 post-Baseline efficacy or exploratory measurements.

Per Protocol Set (PPS): All FAS subjects who received at least 5 of the 7 doses of Study Drug, did not receive antihypertensive medications during the Treatment Period and prior to Study Day 43, and have no significant protocol deviations that would be expected to affect efficacy or exploratory assessments.

Safety Set: All subjects who are randomized and receive at least 1 dose of Study Drug.

PK Set: All subjects who are randomized and receive at least 1 dose of Study Drug and have at least 1 evaluable PK sample.

10.4. Definition of Baseline

The baseline for plasma AGT will be define as the average of all values on or after Study Day -7 and prior to the first dose of Study Drug. The baseline for all other assessments will be defined as the last non-missing measurement prior to the first dose.

10.5. Interim Analysis

An interim analysis may be conducted after at least 50% of the subjects have been enrolled.

10.6. Planned Methods of Analysis

All CRF data, lab data transfers, and any outcomes derived from the data will be provided in the subject data listings. Subject data listings will be presented for all subjects randomized in the study. Descriptive summary statistics including n, mean, median, standard deviation, standard error, interquartile range (25th percentile, 75th percentile), and range (minimum, maximum) for continuous variables, and counts and percentages for categorical variables will be used to summarize most data. Where appropriate, p-values will be reported. All statistical tests will be conducted using 2-sided tests with 5% Type I error rate unless otherwise stated.

10.6.1. Demographic and Baseline Characteristics

Demographic and Baseline characteristics will be summarized using descriptive statistics by treatment group. Subject randomization will be summarized by treatment group. The subject disposition will be summarized. All subjects enrolled will be included in a summary of subject disposition.

10.6.2. Safety Analysis

The safety analysis will be conducted on the Safety Set.

Treatment duration and amount of Study Drug received will be summarized by treatment group. Subject incidence rates of all treatment-emergent AEs will be tabulated by Medical Dictionary for Regulatory Activities (MedDRA) coding system by system organ class, preferred term, relationship to Study Drug, and severity. Narratives of treatment-emergent deaths, serious and significant AEs, including early withdrawals due to AEs, will also be provided.

All treatment-emergent AEs, all treatment-emergent AEs potentially related to Study Drug, all treatment-emergent serious AEs, all treatment-emergent serious AEs potentially related to Study Drug, and treatment-emergent Adverse Event of Special Interest (AESI) will be summarized.

Laboratory tests to ensure subject safety including chemistry panel, complete blood count with differential, coagulation panel, etc., will be summarized by study visits for each treatment group. These safety variables will also be presented as change and percent change from Baseline over time after Study Drug administration, as appropriate.

Vital sign and ECG measures will be tabulated by treatment group. In addition, the number of subjects who experience abnormalities in clinical laboratory evaluations will be summarized by treatment group.

10.6.3. Efficacy Analysis

The primary analysis will be the comparison of percent change from Baseline to Study Week 7 (Study Day 43) in plasma AGT between ISIS 757456 80 mg group and placebo group in the Per Protocol Set. The data will be analyzed using analysis of variance (ANOVA) with treatment and randomization stratification factor (screening AGT concentration) as independent variables. In the case data departs substantially from normality, the nonparametric van Elteren test will be employed instead.

The secondary efficacy analyses will be performed in a similar way to the primary analysis, which include:

- Comparison of change and percent change from Baseline to each schedule post-Baseline visit in AGT between ISIS 757456 80 mg group and placebo group in PPS and FAS
- Comparison of change from Baseline to each schedule post-Baseline visit in in-clinic SBP and DBP between ISIS 757456 80 mg group and placebo group in PPS and FAS

10.6.4. Pharmacokinetic Analysis

The plasma PK of ISIS 757456 (total Full Length ASO, including fully conjugated, partially conjugated, and unconjugated ISIS 757456) will be assessed following SC administration. Non-compartmental PK analysis of ISIS 757456 (total Full Length ASO) will be carried out on each individual subject data set.

Other plasma PK parameters, as appropriate, may be determined or calculated at the discretion of the PK scientist.

Metabolite identification and profiling may be conducted on select plasma samples.

Plasma PK parameters will be summarized using descriptive statistics. Additional details regarding the PK analysis will be described in the Statistical Analysis Plan (SAP).

Analysis of potential exposure-response relationship between plasma AGT and ISIS 757456 exposure (such as C_{trough}) will be conducted. Relationships between other relevant biomarkers and PK measures may also be explored, if deemed appropriate.

Population PK and PK/PD analysis may be performed using PK data from this Study, and/or combined with other ISIS 757456 clinical PK/PD data later in the development timeline.

10.6.5. Exploratory Analyses

The change of the weekly average of at-home BP from Baseline to each schedule post-Baseline visit, and the change and percent change from Baseline to each schedule post-Baseline visit in angiotensin II, renin (Plasma renin activity [PRA]; active renin mass concentration [ARC]), and plasma aldosterone will be compared between ISIS 757456 80 mg group and placebo group in PPS and FAS. The data will be analyzed in a similar way to the primary analysis.

The percentage of subjects reaching the following goals for the in-clinic BP over time will be summarized, comparison of which will be made between ISIS 757456 80-mg group and placebo group using Fisher's exact test.

- Percentage of subjects reaching SBP goal of ≤ 140 mmHg
- Percentage of subjects reaching DBP goal of ≤ 90 mmHg
- Percentage of subjects reaching both goals of SBP ≤ 140 mmHg and DBP ≤ 90 mmHg

In addition, the percentage of subjects requiring antihypertensive therapy during the study, as well as the time in days from first dose of Study Drug to the first administration of antihypertensive therapy during the study will be compared between ISIS 757456 80-mg group and placebo group in PPS and FAS. The analyses will be detailed in the SAP.

11. INVESTIGATOR'S REGULATORY OBLIGATIONS

11.1. Informed Consent

The written informed consent document should be prepared in the language(s) of the potential patient population, based on an English version provided by the Sponsor.

Before a subject's participation in the trial, the Investigator is responsible for obtaining written informed consent from the subject after adequate explanation of the aims, methods, anticipated benefits, and potential hazards of the study and before any protocol-specific screening procedures or any Study Drug (ISIS 757456 or placebo) are administered. The subject must be given sufficient time to consider whether to participate in the study.

The acquisition of informed consent and the subject's agreement or refusal to notify his/her primary care physician should be documented in the subject's medical records and the informed

consent form should be signed and personally dated by the subject and by the person who conducted the informed consent discussion (not necessarily an Investigator). The original signed informed consent form should be retained in the Study Master File and in any other locations required by institutional policy, and a copy of the signed consent form should be provided to the subject.

11.2. Ethical Conduct of the Study

All applicable regulations and guidelines of current Good Clinical Practice (GCP) as well as the demands of national drug and data protection laws and other applicable regulatory requirements must be followed.

11.3. Institutional Review Board

A copy of the protocol, proposed informed consent form, other written subject information, and any proposed advertising material must be submitted to the IRB for written approval. A copy of the written approval of the protocol and informed consent form must be received by the Sponsor before recruitment of subjects into the study and shipment of Study Drug. A copy of the written approval of any other items/materials that must be approved by the Study Center or IRB must also be received by the Sponsor before recruitment of subjects into the study and shipment of Study Drug. The Investigator's Brochure must be submitted to the IRB for acknowledgement.

The Investigator must submit to and, where necessary, obtain approval from the IRB, for all subsequent protocol amendments and changes to the informed consent document. The Investigator should notify the IRB of deviations from the protocol in accordance with ICH GCP. The Investigator should also notify the IRB of SAEs occurring at the Study Center and other AE reports received from the Sponsor, in accordance with local procedures.

The Investigator will be responsible for obtaining annual IRB approval/renewal throughout the duration of the study. Copies of the Investigator's reports, all IRB submissions and the IRB continuance of approval must be sent to the Sponsor.

11.4. Subject Confidentiality

The Investigator must ensure that the subject's confidentiality is maintained. On the case report forms (CRF) or other documents submitted to the Sponsor, subjects should be identified by initials (if permitted by local law) and a subject identification number only. Documents that are not for submission to the Sponsor (e.g., signed informed consent forms) should be kept in strict confidence by the Investigator.

In compliance with Federal and local regulations/ICH GCP Guidelines, it is required that the Investigator and institution permit authorized representatives of the company, of the regulatory agency(s), and the IRB direct access to review the subject's original medical records for verification of study-related procedures and data. Direct access includes examining, analyzing, verifying, and reproducing any records and reports that are important to the evaluation of the study. The Investigator is obligated to inform and obtain the consent of the subject to permit named representatives to have access to his/her study-related records without violating the confidentiality of the subject.

12. ADMINISTRATIVE AND LEGAL OBLIGATIONS

12.1. Protocol Amendments

Protocol amendments must be made only with the prior approval of the Sponsor. Agreement from the Investigator must be obtained for all protocol amendments and amendments to the informed consent document. The regulatory authority and IRB must be informed of all amendments, and the IRB must give approval for any amendments likely to affect the safety of the subjects or the conduct of the trial. The Investigator **must** send a copy of the approval letter from the IRB to the Sponsor.

12.2. Study Termination

The Sponsor reserves the right to terminate the study. The Investigator reserves the right to terminate their participation in the study, according to the terms of the site contract. The Investigator should notify the IRB in writing of the trial's completion or early termination and send a copy of the notification to the Sponsor.

12.3. Study Documentation and Storage

An electronic case report form (eCRF) utilizing an Electronic Data Capture (EDC) application will be used for this study.

The Investigator should ensure that all appropriately qualified persons to whom he/she has delegated trial duties are recorded on a Sponsor-approved Delegation of Site Responsibilities Form.

Source documents are original documents, data, and records from which the subject's CRF data are obtained. These include but are not limited to hospital records, clinical and office charts, laboratory and pharmacy records, imaging, and correspondence. In this study, eCRFs may not be used as source documents.

The Investigator and Study Center staff are responsible for maintaining a comprehensive and centralized filing system of all study-related (essential) documentation in accordance with ICH GCP, suitable for inspection at any time by representatives from the Sponsor and/or applicable regulatory authorities. Elements should include:

- Subject files containing completed CRFs, informed consents, and supporting copies of source documentation
- Study files containing the protocol with all amendments, Investigator's Brochure, copies of pre-study documentation and all correspondence to and from the IRB and the Sponsor
- If drug supplies are maintained at the Study Center, proof of receipt, Study Drug Product Accountability Record, Return of Study Drug Product for Destruction, final Study Drug product reconciliation, and all drug-related correspondence

In addition, all original source documents supporting entries in the CRFs must be maintained and be readily available.

No study document should be destroyed without prior written agreement between the Sponsor and the Investigator. Should the Investigator wish to assign the study records to another party or move them to another location, he/she must notify the Sponsor.

12.4. Study Monitoring

The Sponsor representative and regulatory authority inspectors are responsible for contacting and visiting the Investigator for the purpose of inspecting the facilities and, upon request, inspecting the various records of the trial (e.g., CRFs and other pertinent data) provided that subject confidentiality is respected.

The Sponsor monitor is responsible for inspecting the CRFs at regular intervals throughout the study to verify adherence to the protocol; completeness, accuracy, and consistency of the data; and adherence to local regulations on the conduct of clinical research. The monitor should have access to subject medical records and other study-related records needed to verify the entries on the CRFs.

The Investigator agrees to cooperate with the monitor to ensure that any problems detected in the course of these monitoring visits, including delays in completing CRFs, are resolved.

In accordance with ICH GCP and the Sponsor's audit plans, this study may be selected for audit by representatives from the Sponsor's Clinical Quality Assurance Department. Inspection of Study Center facilities (e.g., pharmacy, drug storage areas, laboratories) and review of study-related records will occur to evaluate the trial conduct and compliance with the protocol, ICH GCP, and applicable regulatory requirements.

To ensure the quality of clinical data a clinical data management review will be performed on subject data received by the Sponsor. During this review, subject data will be checked for consistency, omissions, and any apparent discrepancies. In addition, the data will be reviewed for adherence to the protocol and GCP. To resolve any questions arising from the clinical data management review process, data queries and/or Study Center notifications will be sent to the Study Center for completion and return to Sponsor.

The Principal Investigator will sign and date the indicated places on the CRF. These signatures will indicate that the Principal Investigator inspected or reviewed the data on the CRF, the data queries, and the Study Center notifications, and agrees with the content.

12.5. Language

Case report forms must be completed in English. Generic names and trade names are acceptable for concomitant medications. Combination medications should be recorded using their trade name.

All written information and other material to be used by subjects and investigative staff must use vocabulary and language that are clearly understood.

12.6. Compensation for Injury

The Sponsor maintains appropriate insurance coverage for clinical trials and will follow applicable local compensation laws. Subjects will be treated and/or compensated for any study-related illness/injury in accordance with the information provided in the Compensation for Injury section of the Informed Consent document.

14. APPENDICES

APPENDIX A. SCHEDULE OF PROCEDURES

ISIS 757456-CS2
Protocol

CONFIDENTIAL

Amendment 1
29 March 2019

Appendix A Schedule of Procedures

Study Week	Screen	Run-In	WO			Treatment (6 Weeks)						Post-Treatment Evaluation Period (13 Weeks)					
		Wk -3	Wk -2	Wk -1	Wk1	Wk 2	Wk3	Wk4	Wk5	Wk6	Wk7	Wk8	Wk10	Wk12	Wk16	Wk19	
Study Day	D-42 to D-22	D-21	D-14	D-7	D1	D3	D8	D15	D22	D29	D36	Treatment Early Term ⁹ /D43	D50	D64	D78	D106	PT Early Term ⁹ /D127
Visit Window	N/A		± 1	± 1		+2	+2	± 2	± 2	± 2	± 2	± 2	± 2	± 2	± 5	± 5	± 5
Scheduled Visit #	1	2	3	4	5	6	7	8	9	10	11	12	13	14	15	16	17
Informed Consent	X																
Inclusion/Exclusion	X			X													
Medical History	X																
CVD Risk Factors	X																
Body Weight and Height ⁸	X				X							X					X
Physical Exam ¹	X				X							X					X
ECG (12-Lead)	X				X ^c						X ^c	X					
Vital Signs (clinic) ²	X	X	X	X	X ^a	X ^a	X ^a	X ^a	X ^a	X ^a	X ^a	X	X	X	X	X	X
Home BP/HR ²		X	X	X	X	X	X	X	X	X	X	X	X	X	X	X	X
HIV, HepB & C	X																
FSH ³	X																
Pregnancy Test ⁴	X																
Chemistry Panel (Fasting) ^{7, 11}	X				X ^a	X ^a	X ^a	X ^a	X ^a	X ^a	X ^a	X	X	X	X	X	X
Renal Urine Biomarkers	X				X ^a	X ^a	X ^a	X ^a	X ^a	X ^a	X ^a	X	X	X	X	X	X
TSH, FT3, FT4	X																
Hematology ⁷	X				X ^a	X ^a	X ^a	X ^a	X ^a	X ^a	X ^a	X	X	X	X	X	X
Urinalysis ¹⁰	X				X ^a	X ^a	X ^a	X ^a	X ^a	X ^a	X ^a	X	X	X	X	X	X
Angiotensinogen	X			X	X ^a	X ^a	X ^a	X ^a	X ^a	X ^a	X ^a	X	X	X	X	X	X

ISIS 757456-CS2
 Protocol

CONFIDENTIAL

Amendment 1
 29 March 2019

Appendix A Schedule of Procedures *Continued*

Study Week	Screen	Run-In	WO			Treatment (6 Weeks)						Post-Treatment Evaluation Period (13 Weeks)					
		Wk -3	Wk -2	Wk -1	Wk1	Wk2	Wk3	Wk4	Wk5	Wk6	Wk7	Wk8	Wk10	Wk12	Wk16	Wk19	
Study Day	D-42 to D-22	D-21	D-14	D-7	D1	D3	D8	D15	D22	D29	D36	Treatment Early Term ⁹ /D43	D50	D64	D78	D106	PT Early Term ⁹ /D127
Visit Window	N/A		± 1	± 1		+2	+2	± 2	± 2	± 2	± 2	± 2	± 2	± 2	± 5	± 5	± 5
Scheduled Visit #	1	2	3	4	5	6	7	8	9	10	11	12	13	14	15	16	17
Exploratory	X			X	X ^a				X ^a			X		X	X	X	X
hsCRP					X ^a						X ^a	X					X
PT, INR, aPTT	X				X ^b	X ^a	X ^a			X ^a	X ^a	X					
Study Drug Administration					X	X	X	X	X	X	X						
Adverse Events	X	X	X	X	X	X	X	X	X	X	X	X	X	X	X	X	X
Concomitant Medications	X	X	X	X	X	X	X	X	X	X	X	X	X	X	X	X	X
PK Blood Sampling ⁵					X ^d	X ^a	X ^a	X ^a	X ^a	X ^a	X ^a	X	X	X	X	X	X
Immunogenicity Testing					X ^a							X					X
Archived Serum Sample ⁶					X	X	X			X	X	X			X		X

Run-in = Subjects will measure their SBP/DBP/HR while on their current antihypertensive medications for 1 week prior to withdrawal of HTN medications

WO = Washout from antihypertensive medications (ACE/ARB and any other antihypertensive medications)

If not specifically labeled, "X" means anytime

A 10-minute time window applies to all procedures to allow for flexibility where multiple procedures are scheduled at the same time

- 1 Full physical exam to be given at Screening and abbreviated physical exam to be given thereafter
- 2 Vital Signs (clinic): Blood Pressure (SBP/DPB; sitting), Orthostatic assessment (supine and standing, required at Screening), Heart Rate (HR), Respiratory rate (RR), Temperature (T); Vital Signs (home) = Blood Pressure (SBP/DPB), Heart Rate (HR). Please adhere to the blood pressure guidance document as closely as possible. Home vital sign assessments will be reviewed by the study doctor at each visit prior to dosing. Based on Study Doctor judgment, and in consultation with the Sponsor Medical Monitor, during the Post-Treatment Period and no sooner than 4 weeks after the last dose, the frequency of the home assessments may be decreased.
- 3 Women who are not surgically sterile, as confirmation of menopause
- 4 Women who are not surgically sterile. Serum test to be done
- 5 Refer to [Appendix C](#) for PK sampling schedule

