5.1. Inclusion Criteria

1. Must have given written informed consent (signed and dated) and any authorizations required by local law and be able to comply with all study requirements
2. Males or females aged 18-72 inclusive and weighing $\geq 50 \text{ kg}$ at the time of informed consent

3. Satisfy the following:
 - a. Females: must be non-pregnant and non-lactating, and either:
 - i. surgically sterile (e.g., tubal occlusion, hysterectomy, bilateral salpingectomy, bilateral oophorectomy) or,
 - ii. post-menopausal (defined as 12 months of spontaneous amenorrhea in females > 55 years of age or, in females ≤ 55 years, 12 months of spontaneous amenorrhea without an alternative medical cause and follicle stimulating hormone (FSH) levels in the postmenopausal range for the laboratory involved)
 - b. Males: Surgically sterile (i.e., bilateral orchidectomy) or abstinent*, if engaged in sexual relations with a woman of child-bearing potential (WOCBP), the subject or subject's non-pregnant female partner must be using a highly effective contraceptive method (refer to Section 6.3.1) from the time of signing the informed consent form until at least 13 weeks after the last dose of Study Drug (ISIS 757456 or placebo)

* True abstinence (i.e., refraining from heterosexual intercourse throughout the duration of study participation) is only acceptable. Periodic abstinence (e.g., calendar, ovulation, symptothermal, post-ovulation methods), declaration of abstinence for the duration of a trial and withdrawal are not acceptable methods of contraception
4. Willing to refrain from strenuous exercise/activity (e.g., heavy lifting, weight training, intense aerobics classes, etc.) for at least 24 hrs prior to study visits
5. BMI ≤ 35.0 kg/m²
6. Brachial circumference is ≥ 22 and ≤ 37 cm (8.7 and 14.6 inches)
7. Subject must have been diagnosed with essential hypertension for a minimum of 3 months prior to screening
8. At Screening, the subject must have a plasma AGT concentration ≥ 20 µg/mL
9. At Screening, the subject must have been on a stable regimen of antihypertensive medications (a total of 2) for at least 1 month prior to screening, using either an angiotensin-converting enzyme inhibitor (ACEi) or an angiotensin II receptor blocker (ARB), as well as a single other antihypertensive medication in the following categories:
 - a. beta blocker
 - i. acebutolol (≤ 400 mg q.d.)
 - ii. atenolol (≤ 50 mg q.d.)
 - iii. betaxolol (≤ 10 mg q.d.)
 - iv. bisoprolol (≤ 5 mg q.d.)

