6.3. Restriction on the Lifestyle of Subjects

6.3.1. Contraception Requirements

All male subjects must refrain from sperm donation and either be abstinent[†] or use highly effective contraception from the time of signing the informed consent form until at least 13 weeks after their last dose of study treatment.

For male subjects engaged in sexual relations with a WOCBP either the subject or their female partner must use highly effective contraception from the time of signing the informed consent until 13 weeks after the subject's last dose of study treatment.

For the purposes of this study, WOCBP are defined as any female who has experienced menarche, and who does not meet one of the following conditions:

- Postmenopausal: 12 months of spontaneous amenorrhea in females > 55 years of age or, in females ≤ 55 years, 12 months of spontaneous amenorrhea without an alternative medical cause and FSH levels in the postmenopausal range for the laboratory involved
- 6 weeks after surgical bilateral oophorectomy with or without hysterectomy
- Post hysterectomy

For the purposes of the study, highly effective contraception is defined as follows:

For male subjects:

- Highly effective male contraception includes a vasectomy with negative semen analysis at follow-up, or the non-pregnant female partner of WOCBP uses a highly effective contraceptive method (defined below)
- Male subjects with partners that are pregnant must use condoms as contraception to ensure that the fetus is not exposed to the Study Drug

For female subjects and female partners of male subjects, highly effective female contraception methods comprise:

- Surgical sterilization (e.g., bilateral tubal occlusion), hormonal contraception associated with inhibition of ovulation (combined estrogen and progestogen containing, or progestogen-only), intrauterine contraception device or intrauterine hormone-releasing system (IUS)

†Note: True abstinence (i.e., refraining from heterosexual intercourse throughout the duration of study participation) is only acceptable. Periodic abstinence (e.g., calendar, ovulation, symptothermal, post-ovulation methods), declaration of abstinence for the duration of a trial and withdrawal are not acceptable methods of contraception.

Note: A female condom and a male condom should not be used together as friction between the 2 can result in either or both products failing.

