9.4.3.6. Follow-up of Adverse Event

Investigator Follow-Up

During the study period, the Investigator should follow each AE until the event has resolved to baseline grade or better, the event is assessed as stable, the patient is lost to follow-up, or the patient withdraws consent. Every effort should be made to follow all SAEs considered to be related to Study Drug or related to study procedures until a final outcome can be reported.

Resolution of AE (with dates) should be documented on the Adverse Event eCRF and in the patient's medical record to facilitate source data verification.

Investigator should follow-up or support the Sponsor's effort to follow-up with all pregnancies reported during the study from either the study subject or the female partner of male study subject until pregnancy outcome is available.

Sponsor Follow-Up

For SAEs, AESI and pregnancy cases in subjects who have completed or terminated study, the Sponsor or a designee should follow-up by telephone, fax, email, and/or a monitoring visit to obtain additional case details and outcome information (e.g., from hospital discharge summaries, consultant reports, autopsy reports) in order to perform an independent medical assessment of the reported case.

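### Inclusion 3a and schedule footnote 4 treat tubal occlusion and salpingectomy as sterility while Section 6.3.1 leaves these women of child-bearing potential, so they get no pregnancy test; and Section 9.5.4 gives no initial report for a pregnancy in a female subject

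*Combined protocol and SAP*

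**What the plan says.** **Who may enter.** Protocol Section 5.1, criterion 3a, opens with "Females: must be non-pregnant and non-lactating, and either" and then gives two routes. The first is "surgically sterile (e.g., tubal occlusion, hysterectomy, bilateral salpingectomy, bilateral oophorectomy) or". The second is "post-menopausal (defined as 12 months of spontaneous amenorrhea in females > 55 years of age or", which for women aged 55 or under also needs an FSH level in the post-menopausal range. Criterion 2 sets the age range at 18 to 72.

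**Who is tested.** The schedule in Appendix A has one pregnancy-test entry, at Screening. Footnote 4 limits it: "Women who are not surgically sterile. Serum test to be done". Footnote 3 sends the same group for FSH: "Women who are not surgically sterile, as confirmation of menopause". Appendix B lists serum beta-hCG for women where applicable, which does not widen the group.

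**Who counts as able to bear children.** Section 6.3.1 states that "WOCBP are defined as any female who has experienced menarche, and who does not meet one of the following conditions". The conditions are three: post-menopausal, at least six weeks after bilateral oophorectomy, or after hysterectomy. Neither tubal occlusion nor salpingectomy is among them. The same section names bilateral tubal occlusion as a highly effective contraceptive method for female subjects and for female partners.

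**What happens if a pregnancy occurs.** Section 9.5.4 is triggered as follows: "If a male subject makes or believes that he has made someone pregnant during the study". Its 24-hour form and its outcome follow-up concern the partner of a male subject. Section 9.4.3.6 is wider. It asks the investigator to follow "pregnancies reported during the study from either the study subject or the female partner of male study subject".

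**The concern.** Two notions are in use. Criterion 3a and footnotes 3 and 4 work with surgical sterility, which takes in tubal occlusion and salpingectomy. Section 6.3.1 works with child-bearing potential, from which those two procedures give no exemption. A pre-menopausal woman with either procedure is eligible under the first notion, is a WOCBP under the second, and is left out of the test.

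The protocol treats fetal exposure as a hazard. Section 6.3.1 requires condoms for male subjects whose partner is pregnant, expressly to protect the fetus, and runs male contraception to 13 weeks after the last dose. It sits oddly with this that a woman who is dosed directly, up to seven times, and whom the protocol itself classes as a WOCBP, has no laboratory check of the non-pregnant criterion. If she became pregnant, the section a site would turn to first describes no initial report for her. The stake is participant and fetal safety, not the efficacy result.

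**Working it through.** The plan gives no figure to reproduce and no arithmetic applies. The check sets the passages side by side.

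*Inputs:* criteria 2 and 3a (Section 5.1); the WOCBP definition and the contraception list (Section 6.3.1); the pregnancy-test row and footnotes 3 and 4 (Appendix A); the assay list (Appendix B); Sections 9.4.3.6 and 9.5.4.

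1. Eligible women = surgically sterile women plus post-menopausal women (3a).
2. Eligible women tested = eligible women minus surgically sterile women (footnote 4). What remains is post-menopausal women who have not been sterilized.
3. Eligible women who are WOCBP = eligible women minus those who are post-menopausal, post-hysterectomy or at least six weeks after bilateral oophorectomy (6.3.1). What remains is pre-menopausal women with tubal occlusion or bilateral salpingectomy. The age range admits them.
4. The groups in steps 2 and 3 do not overlap.

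| Eligible woman | Route in 3a | WOCBP under 6.3.1 | Screening test |
|---|---|---|---|
| Not sterilized, post-menopausal | second | no | yes |
| Hysterectomy, or bilateral oophorectomy at least 6 weeks ago | first | no | no |
| Tubal occlusion or bilateral salpingectomy, post-menopausal | either | no | no |
| Tubal occlusion or bilateral salpingectomy, pre-menopausal | first | **yes** | **no** |

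One edge case is left: a pre-menopausal woman less than six weeks after oophorectomy without hysterectomy would also be a WOCBP. It is trivial in practice, since exclusion 1 gives major surgery in the three months before screening as an example of a disqualifying history.

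5. Timing: of 17 scheduled visits, the test is marked at one, Screening (Day -42 to Day -22). No later entry picks up the women in the last row.
6. Reporting: Section 9.5.4 has a trigger, a 24-hour form and outcome follow-up for the partner of a male subject, and no sentence on a female subject. Section 9.4.3.6 has follow-up for both, and no initial form for either. A pregnancy in a female subject thus has follow-up without a stated initial report.

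**The case against.** The best case for the plan is that 3a and footnotes 3 and 4 share one consistent concept, surgical sterility, and that WOCBP does other work. The duties in 3b and 6.3.1 that use the term concern partners of male subjects, and no test for a female subject is keyed to it. Section 6.3.1 itself calls tubal occlusion surgical sterilization. This lowers the weight of the point but does not remove it: 6.3.1 lists contraceptive methods for female subjects too, and its definition covers any female after menarche.

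Several stronger readings are tempting. The documents do not support them.

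- *The test is wasted on women who cannot be pregnant.* It is done at Screening, beside FSH and before eligibility is settled. It can catch a candidate wrongly thought post-menopausal. Only among women who later prove eligible is the tested group confined to post-menopausal women.
- *The untested women carry a material risk of pregnancy.* The documents give no failure rate for either procedure. Their status rests on the 6.3.1 definition alone, and no level of risk can be derived.
- *The non-pregnant criterion is never checked.* Medical history and physical examination take place at Screening, eligibility is reviewed again at Day -7, and Section 4.2 requires investigator verification and Medical Monitor review before randomization. What is missing is a laboratory check.
- *The protocol ignores pregnancy in female subjects.* Section 9.4.3.6 covers follow-up to outcome, and Section 9.3.3 makes a congenital anomaly a serious event whether the subject is male or female, reportable within 24 hours under Section 9.4.1. The gap is the initial report of the pregnancy itself.
- *Section 8.8 contradicts the rest by not naming pregnancy as a ground for stopping Study Drug.* That is an omission, not a contradiction, and any dosing action is for the sponsor.

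**Conclusion.** The point holds as two inconsistencies in the current text. First, 3a and footnote 4 on one side and 6.3.1 on the other disagree on whether tubal occlusion and bilateral salpingectomy end child-bearing potential. As a result, any eligible pre-menopausal woman with either procedure is a WOCBP under 6.3.1 and has no laboratory check of the non-pregnant criterion. Second, 9.5.4 and 9.4.3.6 differ on whose pregnancies are in scope, which leaves a female subject without an initial reporting route.

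The size cannot be computed. The documents do not say how many of the approximately 30 subjects would be women of this kind. An assumed range of 0 to 5 is illustrative only, and zero is possible. The conclusion needs no assumption about risk, only the 6.3.1 definition as written. The primary AGT comparison is unaffected. The protocol should be corrected because the gap touches participant and fetal safety and is cheap to close, but it does not call the design into question.

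**What to change.** Two reconciliations, both for the sponsor to decide on clinical grounds.

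- **Definition.** Bring 3a, Section 6.3.1 and footnote 4 into line so that a single definition decides which female subjects are tested. Either direction would restore consistency: the footnote can follow the 6.3.1 definition, or 6.3.1 can state how tubal occlusion and salpingectomy are to be classed for female subjects. This review does not say which is clinically right, nor whether a single test at Screening is enough.
- **Reporting.** Reconcile 9.5.4 with 9.4.3.6 so that a pregnancy in a female subject has a stated initial report leading into the follow-up that 9.4.3.6 already expects.

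The cost is amendment wording. If the tested group changes, the assay is already listed in Appendix B and blood is already drawn at Screening, so the added laboratory work is small and no visit is added.
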